16.1.7. Percentage Change in Tumor Size

[figure not shown]
Percentage change in tumor size will be determined for patients with measurable disease at baseline and is derived at each visit by the percentage change in the sum of the diameters of target lesions compared to baseline. Best (minimum) percentage change from baseline (PCFB) in tumor size will be summarized by dose cohort and disease cohort using descriptive statistics and a waterfall plot will be presented also. The sum of diameters will be taken from the field “Sum of Diameters of Target Lesions” in “Assessment of Disease (According to RECIST 1.1) (RS)” form of eCRF or be calculated from the field “Measured Diameter” in “Tumor Results: Target Lesion (TARGET)” form of eCRF.

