5.6 Overall Survival Follow Up

Overall survival is defined as the time from the date of the first dose of study drug until the date of patient death (any cause). Investigators and/or delegated site staff should follow patients enrolled to the BTC and STS expansion cohorts, who have signed informed consent under sponsor Amendment 8 (or later), until death or until the patient is lost to follow up. Follow up for OS will begin after the end of treatment (EOT) visit has been completed. Patients should be followed every 8 weeks (\pm 2 weeks) via telephone or in a manner that follows local site SOPs. Site staff should attempt to contact a patient 3 times and consult with authorized family members for the status of the patient (when applicable) before considering a patient lost to follow up. Data to be collected should include the date the patient was last known to be alive, the date of death, and the cause of death.

Treatment completion of patients will occur if any of the following 3 criteria is met:

1. Disease progression (according to RECIST Version 1.1), unless there is reasonable evidence of clinical benefit to justify continuation on the study drug. The continuation decision should be made by the investigators in consultation with the sponsor. The disease progression date is the date when radiological disease progression is first reported according to RECIST Version 1.1 criteria;
2. Death;
3. End of this study.

Early discontinuation of study drug will occur if any of the following criteria is met:

1. Patient withdrawal of informed consent;
2. Intolerable toxicity;
3. Poor patient compliance;
4. Use of other antitumor treatment during the study;
5. Pregnancy occurred during the study treatment period;
6. Patient is lost to follow-up;
7. Treatment discontinuation is in the best interest of the patient based on the assessment of the investigator and sponsor.

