10.6.2 Secondary Efficacy Endpoints

- ORR, defined as the proportion of patients with a best overall response of complete response (CR) and partial response (PR) per RECIST Version 1.1. To be assigned a status of PR or CR, changes in tumor measurements must be confirmed by repeat assessments performed no less than 4 weeks after the criteria for response are first met.
- DCR, defined as the proportion of patients with best overall response of CR, PR, or SD per RECIST Version 1.1.
- TTR, defined as the time between the start date of study drug until first documented response (CR or PR) according to RECIST Version 1.1.
- DoR, defined as the time from the first time that the objective response reaches CR or PR, whichever comes first, until the occurrence of PD or death (if the death of the patient occurs before recording the PD).
- Percent changes of tumor size from baseline of target lesion will be calculated at each visit, and the maximum percent per patient will be selected. Waterfall plots will be used to depict the tumor shrinkage in target lesion. These plots will display the best percentage change in target lesion size.

ORR and DCR will be estimated and 95% exact CIs based on the Clopper-Pearson method will be presented. The time to event endpoints, TTR and DoR will be described in tabular and graphical format using Kaplan-Meier method, including estimated median (in months) with 95% CI, 25th and 75th percentiles.

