16.1. EFFICACY VARIABLE(S) & DERIVATION(S)

16.1.1. Progression-Free Survival

Progression-free survival (PFS) is defined as the time (in months) from the start date of study medication (Day 1) until the date of objective disease progression as defined by RECIST Version 1.1 or death (by any cause in the absence of progression), whichever occurred earlier.

The PFS time will always be derived based on scan/assessment dates and not based on visit dates. RECIST

CCI

assessments/scans contributing towards a particular visit, which consists of assessment for “Non-Target lesions”, “Target lesions”, and “New lesions”, may be performed on different dates. The following rules will be applied:

- Date of progression will be determined based on the earliest of the dates of the radiological component that triggered the progression.
- When censoring a patient for PFS the patient will be censored at the latest of the dates contributing to a particular overall visit assessment.

If a patient has not experienced progressive disease (PD) or died before the end of study for any reason, progression-free survival will be censored at the date of the last evaluable tumor assessment on or prior to the PD, which is not necessarily confirmed.

Three additional rules apply to PFS only:

[figure not shown]
- If a patient misses two or more consecutive tumor assessment visits, and showed PD or death afterwards, PFS will be censored at the date of last tumor assessment prior to the consecutive missed visits. Two consecutive missed/non-evaluable tumor assessment visit window is calculated as $2*(8 \text{ weeks}+1\text{week window time})$, which is 126 days.
- If a patient reports no baseline tumor assessments or has no evaluable tumor assessment visits after the first dose of study medication, PFS will be censored at the start date of study medication unless they die within two consecutive tumor assessments since the first dose of study medication, i.e., PFS=1 day.
- Of note that tumor assessments after the first new anti-cancer treatment (same day inclusive) will be considered inadequate. If a patient starts new anti-tumor therapy initiated prior to documented disease progression or death on study, PFS will be censored at the date of the last tumor assessment prior to or on the date of new anti-tumor therapy.

See Table 1 for the detailed information of event/censoring rules for PFS:

Table 1: PFS Events/censoring rules

Description	Event/Censor	Date of Event/Censor

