16.1.2. Best Overall Response

Best overall response (BOR) will be calculated based on the overall visit responses obtained up until RECIST progression is documented, irrespective of whether patients discontinued study medication. In the absence of RECIST progression, BOR is determined by using visit responses up until the last evaluable overall visit response.

Note, CR or PR response(s) after receiving subsequent anti-cancer therapy will not be included.

A patient's overall best objective response will be determined:

- CR: At least one visit response of CR confirmed by subsequent imaging at least 25 days (4 weeks – 3 days window) later with no evidence of progression between confirmation visits. It is required that there is no other overall response, except CR and NE, between the first CR and the subsequent confirming CR which meet the confirmed CR criteria, i.e. CR-NE-CR is the confirmed CR.
- PR: At least one visit response of PR confirmed by subsequent imaging at least 25 days (4 weeks – 3 days window) later with no evidence of progression between confirmation visits. It is required that there is no other overall response, except CR or PR or NE, between the first PR and the subsequent confirming CR or

CCI

PR which meet the confirmed CR or PR criteria, i.e PR-NE-PR is the confirmed PR. If the first PR followed by SD and no matter the requirement of SD is satisfied or not, i.e. PR-SD-PR, the subsequent PR will not be qualified as confirmed PR.

- SD needs to sustain for at least 8 weeks: Stable disease recorded at least 53 days after start of treatment (8 weeks from start of treatment, and also allowing a 3-day visit window). For example, an overall visit response of SD on day 28 will not be considered as SD.
- PD: Progression, or death in the absence of CR/PR or SD.
- NE: No evidence of CR/PR or SD or PD or death.
- Unconfirmed CR: If the BOR is not qualified as confirmed CR or PR but with at least one visit response of CR prior to subsequent new anti-tumor therapy or PD, then it will be considered as unconfirmed CR.
- Unconfirmed PR: If the BOR is not qualified as confirmed CR or PR but with at least one visit response of PR prior to subsequent new anti-tumor therapy or PD, then it will be considered as unconfirmed PR.

In addition, following special scenarios shall be considered for the determination of BOR:

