- If a patient receives new anti-tumor therapy(s), for that patient, tumor assessments after the first new anti-tumor therapy (same day inclusive) will be considered inadequate, thus not counted towards the determination of BOR.

The table below illustrates the derivation of BOR (with confirmed response) and BOR (regardless of confirmation). Category of confirmed response is dependent on response at the subsequent time-point, and whether the minimum duration criterion for SD has been satisfied.

Overall Response at First Time-point	Overall Response at Subsequent Time-point	SD Sustaining Duration Met at First Time-point	BOR Based on the Two Visits	BOR Regardless of Confirmation (for Unconfirmed CR or PR)
CR	CR	Yes/No	CR	CR
CR	PR	Yes/No	SD/PD	CR (Unconfirmed)
CR	SD	Yes/No	SD/PD	CR (Unconfirmed)
CR	PD	Yes/No	SD/PD	CR (Unconfirmed)

CR	NE	Yes/No	SD/NE	CR (Unconfirmed)
PR	CR	Yes/No	PR/PR	PR
PR	PR	Yes/No	PR	PR
PR	SD	Yes/No	SD/SD	PR (Unconfirmed)
PR	PD	Yes/No	SD/PD	PR (Unconfirmed)
PR	NE	Yes/No	SD/NE	PR (Unconfirmed)
NE	NE	Yes/No	NE	NE

CR = Complete Response; NE = Not Evaluable; ORR = Objective Response Rate; PD = Progressive Disease; PR= Partial Response; SD = Stable Disease.

For patients who progress and subsequently have a response, then the best objective response is only derived from assessments up to and including the time of the progression (i.e., it will not include the response after the patient has progressed).

Tumor response data for dosed patients that had non-measurable disease at baseline (i.e. did not meet study inclusion criteria 7) will be flagged and reviewed according to procedures described in Appendix 3 of the protocol.

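### Best percentage change in tumour size has no stop at progression or at new anti-tumour therapy, although best overall response has both

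*SAP*

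**What the plan says.** **Tumour size.** Percentage change from baseline in tumour size is a secondary efficacy endpoint in both phases (Protocol 4.1.4 and 4.2.4). SAP 16.1.7 says that it "is derived at each visit by the percentage change in the sum of the diameters of target lesions compared to baseline". It then reduces the visits to one value per patient: "Best (minimum) percentage change from baseline (PCFB) in tumor size will be summarized by dose cohort and disease cohort using descriptive statistics". No end of the assessment window is given.

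**Best overall response.** SAP 16.1.2 gives a window: "Best overall response (BOR) will be calculated based on the overall visit responses obtained up until RECIST progression is documented". For a patient who responds after progressing, "the best objective response is only derived from assessments up to and including the time of the progression". Scans on or after the first new anti-tumour therapy "will be considered inadequate, thus not counted towards the determination of BOR".

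**PFS.** SAP 16.1.1 also disregards scans after new therapy, but introduces that rule with "Three additional rules apply to PFS only".

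**Scans after progression.** Protocol 5.6 ends treatment at RECIST progression "unless there is reasonable evidence of clinical benefit to justify continuation on the study drug". The opening text of SAP 16 runs scheduled assessments until progression. It also accepts the treatment-completion scan for all efficacy endpoints, subject to the rules in 16.1. Protocol 5.5 covers patients who stop drug without progression: their scans continue until progression, new therapy or withdrawal of consent.

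**The concern.** The SAP sets its cut-offs endpoint by endpoint, and tumour size has none. A programmer who follows 16.1.7 literally would take the minimum over every target-lesion sum in the database. That includes sums measured after progression has been declared or after another anti-tumour treatment has begun. Shrinkage at those times would be shown as the patient's best result on study drug, although the SAP excludes the same scans from best overall response. The cohorts are small and open-label, the investigator assesses response (Protocol 8.2.1), and SAP 16.4 plans no sensitivity analysis that would show the effect.

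**Working it through.** **1. Plan figures.** The documents state no sample size, power or threshold for tumour-size change, so there is no figure to reproduce. The decision rules in Protocol 10.1 count patients free of progression or death. As binomial tail probabilities P(X ≥ r | n, p), they reproduce as stated:
- 9 of 30 at 15% and 40%: 2.8% and 90.6%
- 6 of 15 at 19% and 50%: 4.9% and 84.9%
- 3 of 10 at 10% and 40%: 7.0% and 83.3%

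None of them uses tumour size.

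**2. The SAP's windows side by side.**

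| Derivation | Stops at progression | Stops at new therapy |
|---|---|---|
| PFS (16.1.1) | Yes, as the event | Yes, in a rule confined to PFS |
| Best overall response (16.1.2), and so ORR and DCR | Yes | Yes, same day included |
| Duration of response (16.1.6) | Yes, as the event | Yes, through the PFS censoring time |
| Tumour size (16.1.7) | Not stated | Not stated |

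**3. How a later scan can exist.**
- *After progression:* the patient continues drug under the clinical-benefit exception in Protocol 5.6 and is scanned again. SAP 16.1.2 itself provides for a response after progression.
- *After new therapy:* the treatment-completion visit falls 30 ± 7 days after the last dose (SAP 7.3), and other therapy can start before it. SAP 17.1 allows for this by ending the adverse-event window at new therapy if that comes first.
- SAP 5.2 cut off tumour data after end of treatment for the interim analysis. SAP 5.4 states no such limit for the final analysis.

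**4. Direction.** Let B be the baseline sum and S the sum at a visit. Change = 100 × (S − B) / B, and the best value is the minimum over admissible visits. If visits are added to a set, the minimum of the larger set is less than or equal to the minimum of the smaller one. Later scans therefore deepen the recorded shrinkage or leave it unchanged.

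**5. Illustration.** The measurements are assumed, with B = 100 mm. Scans at Cycle 2, 4 and 6 Day 1 fall on days 1 + 28 = 29, 1 + 3 × 28 = 85 and 1 + 5 × 28 = 141.

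| Patient | Sums (mm) | Minimum, all visits | Minimum with 16.1.2 cut-offs |
|---|---|---|---|
| A: new lesion (progression) at day 85, drug continued, rescanned at day 141 | 92, 90, 65 | −35% | −10% |
| B: no progression, third scan after new therapy | 95, 97, 68 | −32% | −5% |
| D: plain responder | 80, 60, 66 | −40% | −40% |

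Patient A's best overall response is progressive disease, because stable disease needs at least 53 days (16.1.2) and day 29 is too early. The bar for A would nevertheless pass the −30% partial-response mark, as would the bar for B.

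**6. Share of the plot.** One patient is 1/30 = 3.3% of the bars in Arm A and 1/15 = 6.7% in a NET arm. In a sarcoma subtype of 10 or 5 it is 10% or 20%, if the plot is split that way. These are shares of bars, not estimates of bias.

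**The case against.** **Exposure is small.** Scheduled scans end at progression, and for patients who stop early without progression they end at progression or new therapy. Other anticancer therapy is prohibited on study (Protocol 7.3.2). A bar moves only if a later scan exists and its sum is below every earlier one. This stands as a limit on size. It does not close the gap, because those passages govern when scans are collected, not which scans enter the derivation. If they were enough, the explicit exclusions in 16.1.2 would be unnecessary. The day-141 scan for patient A does assume that scanning continues after progression.

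**The output is descriptive and partly transparent.** There is no formal hypothesis testing, and SAP 16 already requires a listing of responses, sums and changes from which a reader could trace a late value. SAP 9 leaves output content to templates that are not in the text reviewed, and one of them might state a window. All of this is fair and lowers the priority, but the derivation belongs in the SAP text.

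**A cut-off will not make every bar agree with best overall response.** This is correct. Target-lesion change ignores new lesions, non-target lesions and confirmation. A patient at −31% on the scan that shows a new lesion keeps that bar under any cut-off that includes progression.

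**A stronger reading.** A reader might infer that protocol and SAP select opposite extremes, because Protocol 10.6.2 says that percent changes "will be calculated at each visit, and the maximum percent per patient will be selected" while the SAP takes the minimum. On a signed scale, patient D would then show −20% rather than −40%. The protocol's next two sentences do not support that reading: they say that the plots depict shrinkage and display the best change. The largest reduction for D is 40%, which is the SAP's −40%. The wording is loose, but the rules do not conflict, and SAP 4.4 has no change to declare.

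**Conclusion.** The gap is real and narrow. As written, 16.1.7 admits target-lesion sums from after progression or new anti-tumour therapy, which 16.1.2 excludes from best overall response. Any effect favours the drug. It is confined to the summary and waterfall plot of a descriptive secondary endpoint. The primary PFS rates, ORR, DCR and the sample-size rules are untouched.

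The number of patients affected is not given and may be zero, in which case nothing changes. The conclusion assumes that the analysis follows 16.1.7 literally and that at least one patient has a later scan with a sum below all earlier ones. The change is worth making because it is cheap and removes a one-directional choice.

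**What to change.** Add one sentence to SAP 16.1.7: best percentage change uses evaluable target-lesion assessments up to and including first RECIST progression and before the start of any new anti-tumour therapy (same-day scans excluded), as in 16.1.2. Report later values in a listing only. A footnote to the waterfall plot should say that a bar can still differ from best overall response because of new lesions, non-target lesions or lack of confirmation.

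Optionally, reword Protocol 10.6.2 to the largest percent decrease, or the smallest increase if there is no decrease. This clarifies the wording and does not change the analysis.

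The cost is a sentence and a filter on dates already derived for best overall response. The downside is that the waterfall plot may look slightly less favourable.

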16.2. PRIMARY ANALYSIS OF EFFICACY VARIABLE(S)

For each dose level in dose escalation phase and each disease cohort in dose expansion phase, PFS will be described in tabular and graphical format using Kaplan-Meier methods, including estimated median (in months) with 95% CI, 25th and 75th percentiles, minimum, maximum. The 95% CI for the median survival time will be derived using the log-log transformation based on Brookmeyer and Crowley method.

Besides, Kaplan-Meier estimated probabilities with corresponding 80% and 95% CIs at several time points

CCI

(including 4 Months/ 16 Weeks and 11 months) will also be provided and the 80% and 95% CIs will be derived using the log-log transformation based on Greenwood's formula.

Censoring reasons will also be summarized by categories that will be determined using the treatment completion page, the study evaluation completion page and survival page.

The other endpoints including TTR and DoR will be analyzed in the same way where appropriate. In case the number of responses in each treatment group is very small, DoR and TTR may be listed only.

ORR and DCR will be estimated and 95% exact confidence intervals (CIs) based on the Clopper-Pearson method will be presented.

The time to event/censoring and the censoring status for PFS will be listed for the SAS, and for DOR and BOR will be listed for the EAS.

16.3. EXPLORATORY EFFICACY

16.3.1. Tumor Markers

Tumor markers may include, but are not limited to, serum CEA and CA 19-9 (patients with BTC) serum chromogranin A (CgA) and neuron-specific enolase (NSE) for patients with pNET and epNET; and serum or plasma VEGF for all diseases cohorts. Assessment of tumor markers will be performed within 28 days prior to the start of treatment with study drug (C1D1) and at each tumor assessment visit.

The values and change from baseline in tumor markers will be summarized by disease cohort (BTC, pNET, or epNET, or STS) using descriptive statistics. The individual tumor marker test results will be listed by dose cohorts in each phase and by patients. Other exploratory analyses may be performed as appropriate.

16.3.2. Overall Survival

Overall survival (OS) (in months) is defined as the time interval between the start date of study drug and the date of patient death (any cause). The final known date alive will be used as the censoring date for patients who have not been reported to have died by the time of analysis cut-off date. OS will be analyzed for only the BTC and STS cohorts based on the SAS.

Patients who fail to provide any follow-up information will be censored on the date of enrolment. OS (months) will be calculated as (Date of death – start date of study medication + 1) / 30.4375.

CCI

Median, 25th and 75th Quartiles, minimum and maximum will be provided for OS. Kaplan-Meier estimated probabilities with corresponding 80% and 95% CIs at several time points (including 16 weeks, 6 months, 8 months and 11 months for BTC and STS cohort) will be provided. Kaplan-Meier curves will be constructed to provide a visual presentation of the OS change with time.

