6.1. ALL PATIENTS ENROLLED SET [ENR]

The all patients enrolled set (ENR) will include all patients who signed informed consent form (ICF) for this study.

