6.2. SAFETY ANALYSIS SET (SAS) – (ALL TREATED POPULATION)

This analysis set includes all patients who have received at least one dose of surufatinib. Safety data will be evaluated based on this analysis set outcome. Patients in the SAS will be analyzed by their actual dose initially received. If patients have dose reduction during the study, all data will be summarized/ analyzed based on the initial dose of study medication received.

All safety analyses except for DLT summaries will be based on the SAS. Efficacy endpoints PFS and OS (OS applies to BTC and STS cohorts only) will be analyzed based on this analysis set.

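### OS is timed from first dose, but patients without follow-up are censored at an undefined enrolment date that can fall before first dose

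*SAP*

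**What the plan says.** The OS rules are in SAP 16.3.2.

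- **Time origin:** "Overall survival (OS) (in months) is defined as the time interval between the start date of study drug and the date of patient death".
- **Population:** "OS will be analyzed for only the BTC and STS cohorts based on the SAS". SAP 6.2 defines the SAS: "This analysis set includes all patients who have received at least one dose of surufatinib".
- **General censoring rule:** "The final known date alive will be used as the censoring date for patients who have not been reported to have died" by the analysis cut-off.
- **Fallback censoring rule:** "Patients who fail to provide any follow-up information will be censored on the date of enrolment".
- **Formula:** "OS (months) will be calculated as (Date of death – start date of study medication + 1) / 30.4375". It is written for deaths; no formula is given for censored patients.

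The SAP does not define a date of enrolment. The nearest definition is the enrolled set in SAP 6.1, which "will include all patients who signed informed consent form (ICF) for this study".

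For PFS, SAP 16.1.1 treats the comparable case differently. With no baseline or no evaluable post-dose tumour assessment, and no early death, "PFS will be censored at the start date of study medication". Table 1 of the SAP repeats this.

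Protocol 10.6.3 contains only the last-known-alive rule for OS. The enrolment fallback appears in the SAP alone.

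**The concern.** A censoring date should not precede the time origin. Every patient in the OS analysis took at least one dose and was therefore alive on Day 1, so a date before first dose carries less information than the data already hold. If enrolment means consent, the fallback can produce a survival time of zero or below.

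At stake are the OS minimum, which SAP 16.3.2 asks to be reported, and possibly the number of patients counted, if the analysis program does not accept such times. SAP 16.4 plans no sensitivity analysis that would bring this to light.

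A second weakness is that the trigger, having no follow-up information, is undefined. Protocol 5.6 starts OS follow-up only after the end-of-treatment visit, and only for BTC and STS patients who consented under Amendment 8 or later. A programmer could take the trigger to mean no contact of that kind.

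**Working it through.** The documents give no OS figure to reproduce, so the check is date arithmetic.

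**Inputs**

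- Origin: first dose (SAP 16.3.2).
- Months formula: (date B - date A + 1)/30.4375 (SAP 7.7). SAP 16.1.1 uses the same form explicitly for censored PFS; I carry it over to censored OS.
- Enrolment taken as consent (SAP 6.1).
- Consent comes before study-specific screening, and screening falls within 28 days of first dose (Protocol 8.3.1; Synopsis, Visit Frequency). I take 28 days as the practical limit.

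**Check of the convention.** Censoring at first dose gives 0 + 1 = 1 day, or 1/30.4375 = 0.033 months. This agrees with the one-day value that SAP 16.1.1 gives for PFS.

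**Fallback rule**

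| Enrolment before first dose (days) | Time (days) | Time (months) |
|---|---|---|
| 0 | 1 | 0.033 |
| 1 | 0 | 0.000 |
| 2 | -1 | -0.033 |
| 7 | -6 | -0.197 |
| 14 | -13 | -0.427 |
| 28 | -27 | -0.887 |

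The time is zero at a gap of one day and negative at two or more.

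**Against the neighbouring rules.** For a treated patient the last date known alive is never before first dose, so the general OS rule gives at least 0.033 months. The PFS rule gives exactly 0.033. The enrolment rule agrees with them only if enrolment and first dose fall on the same day.

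**Effect on Kaplan-Meier estimates.** A patient censored at or before Day 1 is in no later risk set, whichever of these values is used. As an illustration, I took 28 simulated deaths (exponential with mean 8 months, shifted by 0.2 months) and added 2 such patients at -0.887, 0 or 0.033 months. In all three cases the estimates were 0.679 at 16 weeks, 0.536 at 6 months, 0.393 at 8 months and 0.250 at 11 months. Only the minimum changed.

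**Effect on the count.** If one such patient were not counted, the displayed number would fall by 1 of about 30 in BTC (3.3%) or 1 of about 55 in STS (1.8%).

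**The wider reading of the trigger.** Protocol 5.2 shows that BTC patients were already on study at Amendment 7, before OS follow-up existed. If lack of post-treatment contact triggers the fallback, such patients lose all their known time on treatment while deaths on treatment still count. Taking survivors out of the risk sets and keeping the deaths lowers the curve. The documents do not say how many patients this would be, or whether they consented again later, so I give no size.

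**The case against.** The strongest reply is that a negative time is only one reading. SAP 6.1 defines a set of patients, not a date. Protocol 8.3.1 places enrolment after consent. Elsewhere the protocol uses enrolment and first dose interchangeably for one requirement: compare 6.1 (criterion 5) with 7.3.1 on the stable somatostatin-analogue period, and 3.2 with 6.1 (criterion 8) on the 12-month progression window. If enrolment is the day of first dose, the time is one day and nothing is wrong. This stands as a limit on the claim: the rule can give a time of zero or less, but need not.

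The printed OS formula covers deaths only, so -0.89 months rests on the general formula and the PFS analogy. That also stands.

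The general rule already gives every treated patient a date on or after Day 1, so few or none should need the fallback. This limits the effect, but it leaves two sentences in one section giving different dates for the same patient.

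A reader might infer more: that affected patients silently leave the analysis, that the loss is 1 of 10 in a sarcoma subtype, or that the OS curves are biased. The documents support none of these. They do not say how the software treats such times, and a retained negative time would show in the reported minimum. OS is specified for the BTC and STS cohorts, while subtype summaries are optional (Protocol 10.3). For a patient with truly no post-dose contact, the later estimates do not move.

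**Conclusion.** The fallback rule is wrong as written, and the consequence is small. It can place the censoring date before the time origin, by up to about 28 days if enrolment means consent, and it disagrees with both the last-known-alive rule beside it and the PFS rule. The lowest time, about -0.89 months, assumes that meaning of enrolment, the 28-day screening limit, and the SAP 7.7 formula applied to censored OS.

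OS is exploratory and there is no formal hypothesis testing. On the narrow reading, the damage is confined to the reported minimum and possibly the number analysed. Only the wider reading of missing follow-up could move the curves. The text permits that reading but does not require it.

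**What to change.** In SAP 16.3.2, replace the enrolment date with *the later of the start date of study medication (Day 1) and the last date known alive*. Add the formula for censored patients: (censoring date - start date of study medication + 1)/30.4375.

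The smallest possible time is then 1 day (0.033 months), the rule agrees with PFS, and time known alive on treatment is kept whether or not post-treatment contact took place. Naming the last date known alive, rather than first dose alone, is what closes the wider reading.

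The cost is one or two sentences in the SAP and the matching line of programming. Design and data collection do not change.
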